9.7.3.1. Pregnancy Reporting Rates

The denominator for calculating reporting rates of negative pregnancy outcomes will include prospective reports where prospective registration is defined as a report of a pregnancy exposed to nusinersen enrolled before the outcome of the pregnancy is known (see Section 9.9, which discusses potential biases).

9.7.3.1.1. Spontaneous Abortion

The prevalence of spontaneous abortion reported to the study will be calculated by dividing the number of fetal losses occurring at < 20 weeks of gestational age by the total number of pregnancies. If sufficient enrollment numbers are obtained, analysis of spontaneous abortions may be stratified by earliest trimester of exposure, gestational age at enrollment, maternal age, medical condition that may result in negative pregnancy outcomes, and other maternal risk factors, as appropriate. Sensitivity analyses may be performed for spontaneous abortions and may be stratified by each trimester, along with these factors, when the sample size allows.

The 95% CIs for spontaneous abortion rates will be calculated based on the binomial distribution. If sufficient enrollment numbers are obtained, spontaneous abortion rates may also be presented in subgroups by the earliest trimester of exposure, gestational age at enrollment, maternal age, medical condition, and other maternal risk factors at enrollment, as appropriate.

In addition, time to spontaneous abortion will be analyzed using the Kaplan-Meier method.

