9.2. Setting

Patients with SMA who are enrolled in the ISMAR-US, UK Adult SMA-REACH, and SMArtCARE SMA registries will be informed of the pregnancy study and encouraged to participate if they become pregnant within the relevant exposure window for nusinersen. The registries will collect information on the pregnancy and birth outcomes.

Reporting of pregnancy exposures to nusinersen is voluntary. Pregnancies should be reported as early as possible, ideally before prenatal testing beyond confirmatory pregnancy tests (e.g., alpha fetoprotein, sonography, amniocentesis) has been performed, but pregnancies that are reported after informative prenatal testing has been conducted will also be included in the study. Patients who test positive for a medical condition associated with negative pregnancy outcomes (e.g., syphilis) may also enroll in the study. Pregnancies with known outcomes at the time of the initial report (i.e., retrospective cases) will be included in this study but will be analyzed separately from cases in which the pregnancy outcome is unknown at the time of enrollment (i.e., prospective cases).

Pregnancies in partners of male patients who were exposed to nusinersen will not be included in the study but will be collected according to standard postmarketing pharmacovigilance practice.

The eligibility criteria and data captured in the study are intended to be uniform across all countries in which the study will be conducted. Any changes to eligibility criteria or data collection imposed by a local IRB or ethics committee will be noted in interim and final study reports.

Scientific oversight of the pregnancy study will be the responsibility of Biogen Epidemiology, while data collection and conduct of the ongoing registries will be managed by the registries.

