9.2.2.1. Inclusion Criteria

- 1. Individual who is currently pregnant (or was pregnant during the relevant exposure window; see inclusion criterion 4) and enrolled in the ISMAR-US, UK Adult SMA-REACH, or the Germany, Austria, or Switzerland network of the SMArtCARE registry.
- 2. Ability of the participant and/or their legally authorized representative (e.g., parent, spouse, or legal guardian), as appropriate and where allowed by local regulations, to understand the purpose and risks of the study, to provide informed consent, and to authorize the use of confidential health information in accordance with national and local privacy regulations.
- 3. Genetic documentation of 5q SMA.
- 4. Documentation that the participant was exposed to nusinersen up to 14 months prior to the first day of their LMP before conception, 14.5 months before conception, and/or at any time during their pregnancy. If exact exposure dates are CONFIDENTIAL

unknown, the reporter must be able to estimate either the months of exposure during pregnancy or the trimester of exposure.

5. Agreement to release medical information, thereby permitting the registry to contact the participant's HCPs and the pediatric HCP for medical information.

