9.3.1. Variable Definitions

9.3.1.1. Pregnancy Loss

9.3.1.1.1. Pregnancy Termination

A pregnancy termination is defined as any induced or voluntary fetal loss during pregnancy. If possible, the reason for pregnancy termination (e.g., related to SMA, nusinersen, other) should be collected. If available, data from gross or pathologic examination of the abortus or fetus will be evaluated for structural or chromosomal defects.

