9.7.3. Methods of Analysis

Each pregnancy outcome will be classified into the categories described in Section 9.3 and will be collected and reported separately. Data will be presented in aggregate tables in the interim and final reports.

All analyses will be conducted on an overall basis, as well as stratified by earliest trimester of exposure. For MCMs, analyses will be conducted only for participants who have exposure in the first trimester. The prevalence and 95% CIs of spontaneous abortions, MCMs, SGA births, and abnormal postnatal growth and development will be CONFIDENTIAL

The information contained herein may not be used, disclosed, or published without the written consent of Biogen MA Inc.

calculated. Other negative pregnancy outcomes will be similarly examined as the sample size permits. Infants with minor malformations, chromosomal abnormalities, genetic syndromes, positional defects, and prematurity-related defects will be excluded from the primary analyses related to MCM prevalence; these outcomes will be reported in the interim and final reports. Details of the analysis will be provided in the statistical analysis plan.

If sufficient enrollment numbers are obtained, analyses will also be stratified according to maternal age, gestational age at enrollment, medical condition at time of pregnancy that may affect pregnancy outcome (including but not limited to respiratory, neuropsychiatric, metabolic, cardiovascular, infectious, hematological disease or impairment), and other important risk factors (e.g., concurrent medications and substance use).

Demographic information, clinical characteristics, and other potential factors that may affect pregnancy outcome will be described.

The actual date of delivery (not the EDD) will be used in all analyses. EDD will only be used to schedule outreach to HCPs to ascertain the outcome of an expected birth.

For each interim analysis, pregnancy and infant outcomes will be analyzed cumulatively from the beginning of the study.

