9.9. Limitations of the Research Methods

Although measures will be taken to ensure that the study is methodologically robust, certain limitations should be acknowledged.

Estimating an accurate rate of early spontaneous pregnancy losses is difficult in voluntary pregnancy studies. Spontaneous abortions are likely to occur before the pregnancy is recognized. Even if the pregnancy is recognized, it may not be reported if the spontaneous abortion occurred prior to study enrollment. As such, there will likely be a reporting bias leading to an underestimation of the true early pregnancy loss rate. To address this bias, the study will evaluate pregnancy losses as a function of gestational age at enrollment into the study. Furthermore, inclusion of pregnancies whose outcome is known prior to registration may permit a fuller accounting of spontaneous abortions, though these pregnancies will not be included in the primary analyses to avoid the introduction of recall bias (e.g., participants with negative pregnancy outcomes may be more likely to report information about their pregnancies than participants with normal pregnancy outcomes) [Gliklich 2014]. Finally, pregnancy outcomes that occur outside the study will be collected as part of routine pharmacovigilance practice. These spontaneous reports will be analyzed outside of this study to determine whether there is a signal for an increased risk of adverse outcomes in early pregnancy, including spontaneous pregnancy loss.

Reporting pregnancy outcomes is voluntary, and it is possible that not all participants will complete all follow-up assessments. Enrolled pregnancies for which outcome information is unobtainable will be considered lost to follow-up. It is possible that outcomes from pregnancies lost to follow-up could differ from those with documented outcomes. Because of differences in follow-up and reporting patterns, it is currently not possible to assess with certainty what effect the potential biases of the loss to follow-up may have on the analysis. However, comparisons of the characteristics of each group will be conducted in an attempt to address this potential source of bias.

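### The spontaneous abortion rate uses every prospective pregnancy as denominator, whatever the gestational age at enrolment, so late entry biases it downward

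*Protocol*

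**What the plan says.** Protocol 9.7.3.1.1 defines the prevalence of spontaneous abortion by "dividing the number of fetal losses occurring at < 20 weeks of gestational age by the total number of pregnancies". Section 9.7.3.1 sets the population: "The denominator for calculating reporting rates of negative pregnancy outcomes will include prospective reports where prospective registration is defined as a report" made before the outcome is known. Retrospective cases are therefore out, and there is no further restriction.

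Eligibility has no gestational-age ceiling. Inclusion criterion 1 in 9.2.2.1 reads "Individual who is currently pregnant (or was pregnant during the relevant exposure window; see inclusion criterion 4". Section 9.2 asks for early reporting but states that "pregnancies that are reported after informative prenatal testing has been conducted will also be included in the study". Section 9.3.1.1.2 confines spontaneous abortion to natural losses before 20 weeks.

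Section 9.7.3.1.1 adds that "time to spontaneous abortion will be analyzed using the Kaplan-Meier method". It gives no time origin, entry rule or censoring rule, and 9.7.3 says "Details of the analysis will be provided in the statistical analysis plan".

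Section 9.9 expects the early loss rate to be underestimated and says that "the study will evaluate pregnancy losses as a function of gestational age at enrollment into the study". In 9.7.3 and 9.7.3.1.1, stratification by gestational age at enrolment depends on sufficient numbers. Section 9.5 expects 20 pregnancies in 10 years. Section 9.9 also describes comparisons with EUROCAT and MACDP as robust, and extends this to spontaneous abortion.

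**The concern.** The ratio treats every prospective pregnancy as if it had been observed from the start of the risk period. Two groups break that assumption. Pregnancies enrolled at 20 weeks or later cannot have the event. Pregnancies enrolled earlier, but after risk has begun, have already survived part of it, and losses before enrolment cannot enter the numerator.

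The other main outcomes have denominators closer to the population at risk: malformations use births after first-trimester exposure, and small-for-gestational-age births and postnatal outcomes use live births.

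Section 9.7.3.2 allows the rate to be compared with general-population rates by inspecting point estimates and 95% CIs. A rate that is low because of enrolment timing could be read as reassurance and could mask a real increase.

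**Working it through.** **Inputs from the protocol.** Estimator and population: 9.7.3.1 and 9.7.3.1.1. Event limit of 20 weeks: 9.3.1.1.2. Background miscarriage risk of 15% to 20% in clinically recognised pregnancies: 7.1.2, used here only as a plausible true risk. Expected size of 20 pregnancies: 9.5. That figure is a feasibility count with no precision target, so there is no planned rate to reproduce.

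**Assumptions, because the protocol is silent.** The distribution of gestational age at enrolment, and how the hazard of loss is spread over weeks 5 to 20.

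**Formula.** Let S(w) be the probability that the pregnancy is not lost by week w. A pregnancy enrolled at week a < 20 has remaining risk 1 − S(20)/S(a); one enrolled at a ≥ 20 has remaining risk 0. The expected crude rate is the average of these over the entry weeks.

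**Worked case.** True risk 20% from week 5, weekly hazard weights falling as exp(−0.15 × weeks), entry at weeks 8, 12, 16 and 22 in equal parts. Then S(8) = 0.9136, S(12) = 0.8503, S(16) = 0.8175 and S(20) = 0.8000.

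- Remaining risks: 0.1243, 0.0592, 0.0214 and 0.
- Protocol ratio: (0.1243 + 0.0592 + 0.0214 + 0)/4 = 5.1%.
- Entries before 20 weeks only: 0.2049/3 = 6.8%.
- Kaplan-Meier from LMP without delayed entry, nothing censored before week 20: 5.1%, identical to the crude ratio.
- Kaplan-Meier with entry at enrolment (simulation, 200,000 pregnancies): 12.3%, against a true risk from week 8 of 12.4%.

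Delayed entry therefore recovers risk from the earliest entry week onward, not the full 20%.

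**Range.** Crude rate as a share of a true 15% to 20% risk from week 5, with the hazard flat or declining at 0.15 or 0.3 per week:

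| Assumed entry weeks (equal parts) | Crude / true |
|---|---|
| all at 5 | 1.00 |
| 6, 8, 10, 12 | 0.38 to 0.75 |
| 8, 12, 16, 22 | 0.14 to 0.42 |
| 10, 22 | 0.11 to 0.35 |
| 12, 16, 22, 28 | 0.04 to 0.21 |

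**Second hazard shape.** Put 80% of losses before week 13 and compare with the true risk from week 6, 13.7% to 18.4%. Uniform entry over weeks 6 to 12 gives a crude rate of 9.7% to 13.0%, about 70% of the true rate. Uniform entry over weeks 6 to 28 gives 3.5% to 4.9%, about one quarter; restricting that case to entry before 20 weeks gives 5.5% to 7.5%.

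**What it means at n = 20.** In the worked case the chance of no observed loss is 0.949^20 = 35%. If all 20 carried the full 20% risk it would be 0.80^20 = 1.2%. Zero of 20 has an exact 95% CI of 0% to 16.8%, which excludes 20%.

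**Cost of the correction at n = 20.** With entry over weeks 6 to 28, delayed-entry Kaplan-Meier returns exactly 0% in 36% to 48% of simulated studies. Its central 95% range is 0% to 58% at 15% risk and 0% to 68% at 20% risk. Its root-mean-square error is 0.185 against 0.109 for the crude ratio at 15% risk, and 0.204 against 0.141 at 20%.

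**The case against.** The strongest reply is that the study is small and descriptive, and already discloses the problem. Section 9.7.3.1 refers the reader to 9.9, which names the direction of the bias. Section 9.9 offers evaluation by gestational age at enrolment, retrospective cases for a fuller count, and pharmacovigilance review outside the study. External comparison is optional. This lowers the stakes, but none of it changes the overall estimate: the first measure is conditional in the methods sections and hardly workable with 20 pregnancies, and the other two lie outside the primary analysis.

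The precision objection also stands. At n = 20 the delayed-entry estimate removes nearly all of the bias but has the larger error, so it should not be the only primary estimate.

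Some stronger readings are tempting but not supported:

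- A reader might infer that the Kaplan-Meier analysis ignores delayed entry. The protocol neither specifies nor excludes it, and leaves detail to an SAP that was not available here.
- A reader might infer that the rate is necessarily far too low. That depends on enrolment timing, and the bias vanishes if all enrol at week 5.
- A reader might infer that induced terminations are counted, because 9.3.1.1.1 says "A pregnancy termination is defined as any induced or voluntary fetal loss during pregnancy" and the numerator also speaks of fetal losses. But the sentence defines spontaneous abortion, which 9.3.1.1.2 limits to natural causes, and outcomes are reported separately. The wording is loose, and any such error would run upward.
- A reader might object that a third-trimester exposure stratum can only yield zero. Section 9.7.1 classifies by earliest exposure in a window opening 14 months before LMP and allows small strata to be collapsed.
- Pregnancies lost to follow-up are not said to count as non-events; 9.2.5 makes them a separate category.

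**Conclusion.** The concern holds for the crude ratio. The protocol fixes a denominator that includes pregnancies unable to have the event and others observed for only part of the risk period. This is a stated rule with a predictable downward bias, not a detail left to the SAP.

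The size is not known. Under the assumed patterns it runs from none, through about 70% of the true rate for entry over weeks 6 to 12, to about one quarter for entry over weeks 6 to 28, and lower still if most enrol late. These figures rest on assumed entry times and hazard shapes.

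Section 9.9 is also inconsistent with the methods sections, firm where they are conditional. Its claim of robust comparison for spontaneous abortion sits badly with its own admission of underestimation. For the Kaplan-Meier analysis the defensible statement is only that its entry rule is not given and needs to be, because without delayed entry it can reproduce the crude bias.

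**What to change.** - In 9.7.3.1.1, restrict the spontaneous abortion denominator to prospective pregnancies enrolled before 20 weeks, and count only losses meeting 9.3.1.1.2.
- State that Kaplan-Meier uses gestational age as the time scale, with entry at gestational age at enrolment and censoring at last contact or induced termination.
- Report that estimate with its CI and numbers at risk beside the restricted crude ratio, neither standing alone. Compare with background only conditional on the week at which the curve starts.
- Reconcile the conditional stratification in 9.7.3 and 9.7.3.1.1 with the firm commitment in 9.9, and qualify the robust-comparison statement there for spontaneous abortion.

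This is a wording change: LMP, EDD and the date the pregnancy is reported are already collected at enrolment (9.3.2.1). The cost is statistical. Restriction alone removes only part of the bias (5.1% to 6.8% in the worked case, against 12.4% from week 8). With about 20 pregnancies and few at risk in the early weeks, the delayed-entry estimate will have wide intervals.

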9.7.3.1.2. Major Congenital Malformations

The prevalence of MCMs (referred to as birth defects in EUROCAT) reported to the study will be calculated using EUROCAT conventions (http://www.eurocat-network.eu/accessprevalencedata/interpretationguide/calculationofprevalencerates). The prevalence of 1 or more MCMs in addition to the prevalence of specific MCMs will be calculated as follows:

Total Prevalence of Teratologist-Confirmed MCMs = Number of Teratologist-Confirmed Cases / Number of Births (Live and Still)

Other formulas for prevalence may be used to calculate estimates for comparisons to other background rates from other sources.

The analysis of MCM outcomes will be conducted only for participants who have exposure during the first trimester, adjusting for maternal age, medical condition, and other maternal risk factors at enrollment, as appropriate. Sensitivity analyses may be performed for MCMs and may be stratified by each trimester, along with the above factors, when the sample size allows.

The 95% CIs for MCM rates will be calculated based on the binomial distribution.

9.7.3.1.3. Small for Gestational Age Births

The prevalence of SGA births reported to the study will be calculated by dividing the number of SGA births by the total number of live births. If sufficient enrollment numbers are obtained, analysis of SGA births may be stratified by earliest trimester of exposure, gestational age at enrollment, maternal age, medical condition, and other maternal risk factors, as appropriate. Sensitivity analyses may be performed for SGA births and may be stratified by each trimester, along with these factors, when the sample size allows.

The 95% CIs for SGA birth rates will be calculated based on the binomial distribution. If sufficient enrollment numbers are obtained, SGA birth rates may also be presented in subgroups by the earliest trimester of exposure, gestational age at enrollment, maternal age, medical condition, and other maternal risk factors at enrollment, as appropriate.

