7.1.2. Clinical Experience With Nusinersen in Pregnant Women

There are no adequate data on the developmental risk associated with the use of nusinersen in pregnant individuals. There are no data from clinical studies on the use of nusinersen during pregnancy in humans, and there are limited data on the use of nusinersen during pregnancy from the postmarketing setting.

There are no data on the presence of nusinersen in human milk, the effects on the breastfed infant, or the effects of the treatment on milk production. However, based on the available nonclinical data, the risk of nusinersen exposure through breast milk to breastfeeding children is low.

In the US general population, the estimated background risk of major birth defects and miscarriage in clinically recognized pregnancies is 2% to 4% and 15% to 20%, respectively. The background risk of major birth defects and miscarriage for the indicated population is unknown.

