9.3.1.3. Birth Weight (Including Small for Gestational Age)

All live births will be classified as small, appropriate, or large for gestational age using the CDC definition of birth weight below the 10th percentile, between the 10th and 90th percentile, and above the 90th percentile, respectively. An infant's birth weight percentile and size for gestational age categorization will be based on World Health Organization growth charts or country-specific growth charts, as appropriate. Low birth weight (< 2500 g) will also be examined as an adverse pregnancy outcome.

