9.3.1.12. Abnormal Postnatal Growth and Development

Domains of developmental milestones (i.e., social/emotional, language/communication, neurocognitive, movement/physical development milestones) by age up to 52 weeks will be defined by guidelines provided by the CDC [CDC 2020]. As recommended by the

CONFIDENTIAL

CDC, the World Health Organization Growth Charts (suitable for use in the US from birth to 24 months) will be applied for this study, where infant growth measurements will be used to estimate gender-specific weight-for-length, head circumference-for-age, length-for-age, and weight-for-age percentiles.

Postnatal growth deficiency or FTT will be defined as weight in the < 10th percentile for sex and chronological age using international growth reference standards from WHO for children aged 0 to 24 months. Postnatal growth deficiency will be evaluated at 1, 2, 6, 12, 18, and 24 months of age.

Infant developmental deficiency will be defined as failure to achieve developmental milestones for chronological age defined by CDC. Infant developmental deficiency will be evaluated at 1, 2, 6, 12, 18, and 24 months of age.

Developmental milestones will be collected as part of routine clinical practice with pediatrician-determined results of infant status (i.e., below, above, or at age-appropriate achievement) in each of the domains listed above. "Ages and Stages" or similar standardized assessments may be collected for this study if performed as part of routine clinical care. No additional information will be mandated for collection as part of this study.

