9.5. Study Size

The goal of the research initiative is to enroll as many participants with SMA who receive nusinersen during pregnancy (or within the relevant exposure window) as possible. Based on the number of individuals of childbearing potential currently enrolled in the registries or who come of childbearing age over the duration of the study and the number of incident pregnancies observed in the registries to date, the estimated enrollment number over the 10-year study period is 20 pregnancies.

As of August 2024, the UK Adult SMA-REACH registry has approximately 285 genetically confirmed SMA patients with 72 using nusinersen [Walker 2024]. In the SMArtCARE registry, as of May 2021, there were 965 SMA patients enrolled. This includes 147 women of childbearing age, of whom 117 have been treated with nusinersen.

While enrollment may slow over time, some increase in new patients is expected in all of the registries. In addition to newly enrolled patients, younger patients are expected to reach childbearing age over the next few years. Together, these factors should lead to an increase in individuals of childbearing age in the registries, which will increase the likelihood of capturing incident pregnancies.

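### Infant size is placed on percentile charts, but the named estimates are only proportions; a mean z-score with 95% CI should be added beside SGA and growth deficiency

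*Protocol*

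**What the plan says.** Section 9.3.1.3 places every newborn on a chart: an infant's "birth weight percentile and size for gestational age categorization will be based on World Health Organization growth charts" or on country-specific charts. It then groups them: "All live births will be classified as small, appropriate, or large for gestational age", with cuts at the 10th and 90th percentiles. It adds a second weight outcome: "Low birth weight (< 2500 g) will also be examined as an adverse pregnancy outcome".

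Section 9.3.1.12 estimates weight-for-length, head-circumference, length and weight percentiles after birth. Deficiency is defined on weight alone: "Postnatal growth deficiency or FTT will be defined as weight in the < 10th percentile for sex and chronological age". It is evaluated at 1, 2, 6, 12, 18 and 24 months. The same section also covers developmental milestones.

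The analysis sections turn these into proportions. In 9.7.3.1.3 the prevalence of SGA is "calculated by dividing the number of SGA births by the total number of live births". Section 9.7.3.1.4 divides events of abnormal growth and development by live births. Both use 95% CIs from the binomial distribution. Neither names a mean or other continuous summary of weight, percentile or z-score. Section 9.7.3 leaves further detail to the SAP.

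On size, 9.5 states that "the estimated enrollment number over the 10-year study period is 20 pregnancies". Under 9.4 the sponsor receives the registries' data as aggregate summary tables.

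**The concern.** A proportion below the 10th percentile treats an infant at the 11th percentile like one at the 89th. In a large study that loss is affordable. Here about 16 infants are expected, of whom 1 or 2 would fall below the cut if exposure and disease had no effect, so a moderate downward shift of the whole distribution could easily pass unseen. The measurements that would show it are already collected and already converted to percentiles. The length, head-circumference and weight-for-length percentiles do not enter the growth-deficiency definition and have no named estimate of their own.

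The aggregate data flow makes this worth settling in the protocol. If the registries deliver only counts of SGA and growth-deficient infants, the sponsor cannot recover a mean z-score from them later.

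**Working it through.** **Inputs.** Enrolment is 20 pregnancies (9.5). Section 7.1.2 gives the US background risk of "major birth defects and miscarriage in clinically recognized pregnancies is 2% to 4% and 15% to 20%, respectively". The reference SGA proportion is 10%, by construction of a percentile chart. Comparisons are read from point estimates and 95% CIs (9.7.3.2), so whether the CI excludes the reference is the yardstick.

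**Assumptions not in the protocol.** Z-scores are normal with SD 1, any effect is a pure downward shift of d SD, and the binomial interval is the exact one. The protocol gives no precision or power figure for these outcomes, so there is none to reproduce.

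**Live births.** 20 × (1 − 0.20) = 16 and 20 × (1 − 0.15) = 17. Terminations, stillbirths and loss to follow-up lower this; multiple births raise it.

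**Information kept by the cut.** For a cut at c with p = 0.10, c = −1.2816 and φ(c) = 0.1755. Relative to the z-score itself, the binary split keeps φ(c)²/[p(1 − p)] = 0.0308/0.09 = 0.34. All three size classes (10/80/10) would keep 2φ(c)²/0.10 = 0.62, but 9.7.3.1 names no estimate that uses the large class.

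**Precision with 16 infants.** The exact 95% CI is 0.2% to 30.2% for 1 SGA birth and 1.6% to 38.3% for 2. The mean z-score has half-width t(0.975; 15)/√16 = 2.131/4 = 0.53 SD.

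**When the SGA interval signals.** With 16 infants, 4 SGA births give a lower limit of 7.3% and 5 give 11.0%. Five (31%) are therefore needed. With no effect, P(X ≥ 5 | 16, 0.10) = 0.017.

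**Chance that the CI excludes the reference.** Under a shift d the SGA probability is Φ(−1.2816 + d): 15.1% at 0.25, 21.7% at 0.5, 29.8% at 0.75 and 38.9% at 1.0. The SGA column is the binomial probability of reaching the required count. The z-score columns use the noncentral t with noncentrality d√n. The first uses the usual one-sided 2.5%; the second sets the one-sided error equal to that of the SGA rule.

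| Infants | Count needed | Error of SGA rule | Shift (SD) | SGA proportion | Mean z, 95% CI | Mean z, matched error |
|---|---|---|---|---|---|---|
| 16 | 5 | 1.7% | 0.25 | 8% | 15% | 12% |
| 16 | 5 | 1.7% | 0.5 | 26% | 47% | 39% |
| 16 | 5 | 1.7% | 0.75 | 54% | 80% | 74% |
| 16 | 5 | 1.7% | 1.0 | 81% | 96% | 94% |
| 12 | 5 | 0.4% | 0.5 | 10% | 35% | 12.5% |
| 17 | 5 | 2.2% | 0.5 | 30% | 49% | 47% |
| 20 | 6 | 1.1% | 0.5 | 26% | 56% | 42% |

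The matched column separates two effects. At 16 infants most of the gain at 0.5 SD survives matching (13 of 21 percentage points). At 12 infants nearly all of the gap comes from the coarseness of the exact interval. That coarseness also explains why the proportion does better with 17 infants than with 20.

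**The case against.** **This is SAP territory.** Detail is deferred to the SAP, which is not shown, and nothing in the protocol forbids a continuous summary. A reader might infer that none is planned; the documents do not show that. What stands is narrower: the protocol itself fixes estimator, denominator and interval for these two outcomes, and calls for nothing else.

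**The protocol uses more than one cut.** A reader might infer that size is handled solely as above or below the 10th percentile. That is too strong. Section 9.3.1.3 has three classes and a 2500 g threshold, and the outcome in 9.7.3.1.4 also includes developmental milestones. These are still categories, however, and no named estimate uses the scale itself.

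**SGA is a legitimate clinical outcome.** It is named in the abstract and in 8.2.1, so the z-score should not displace it. If harm is confined to the smallest infants, the proportion is the better measure.

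**Data may be incomplete.** Contacts are not mandated (9.2.1), no extra growth information is mandated (9.3.1.12), and incomplete follow-up is expected (9.9). Sixteen is a derived figure for birth, and numbers at 1 to 24 months may be lower.

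**Many intervals.** Birth weight plus three measures at six ages makes 1 + 3 × 6 = 19 intervals. If independent and read as tests against 0, the chance of at least one false exclusion is 1 − 0.95^19 = 62%; correlation would lower it. This objection stands, and it is why the postnatal summaries should be descriptive.

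**The reference is not a drug-free control.** A reader might infer that a mean z-score below 0 would show a nusinersen effect. Section 9.9 says outcomes may differ because of SMA itself, and infants may have SMA. The chart reference is also not peculiar to the z-score, since the SGA proportion has its own 10% reference.

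**Conclusion.** The point holds as a case for supplementing the named estimates. The protocol derives percentiles and then specifies only proportions for infant size. The 10th-percentile cut keeps about a third of the information on a shift in location. With about 16 infants, the mean z-score raises the chance that the 95% CI excludes the reference from 26% to 47% at a 0.5 SD shift and from 54% to 80% at 0.75 SD. Part of that is the conservatism of the exact interval; the matched figures are 39% and 74%.

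These numbers rest on the derived count of 16, on normal z-scores with SD 1 and on a shift of the whole distribution. They do not support replacing SGA. Nor should the 12-infant contrast of 10% against 35% be quoted as information lost, because it falls to 10% against 12.5% once the error rates are equal. With a half-width of 0.53 SD, the mean z-score remains imprecise; it is a better use of the same data, not a cure for the small sample.

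**What to change.** - In 9.7.3.1.3, keep the SGA proportion with its binomial CI as the named outcome. Beside it, report the mean birth-weight-for-gestational-age z-score with n, SD and a t-based 95% CI.
- In 9.7.3.1.4, keep the proportion with weight below the 10th percentile. Add mean z-scores with n, SD and 95% CI for weight, length and head circumference at each scheduled age. State that these are descriptive and not separate tests against 0.
- In 9.4, or in the data specification agreed with the registries, request n, mean and SD of these z-scores in the aggregate tables.

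No new data are needed. The cost is a change of wording, one extra table and several more descriptive intervals. Two cautions belong in the reports: the z-score does not remove confounding by SMA itself, and early postnatal z-scores by chronological age are pulled down by preterm infants.
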